4.4 PREDETERMINED COVARIATES AND PROGNOSTIC FACTORS

GCL thickness/volume and topographical maps, best or worst-seeing eye (eye status) as determined prior to randomization and duration of vision loss at the time of treatment could be significant prognostic factors for the treatment effect.

The baseline LogMAR will also be used as a covariate for analysis of change in LogMAR. Similarly, the baseline of the endpoint being analyzed will be used as the model's covariate.

The investigative site will not be included in the analysis as the number of subjects recruited per site will be very small. However, stratification by geographical area may be performed as a sensitivity analysis. Neighboring countries can be pooled to reach at least 9 subjects per geographical entity. All analysis will be performed using an alpha of 0.05 (two-sided test).

These covariates will be used in the analyses presented in [Section 9.5 Efficacy Analysis](#).

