5.3 CHANGE FROM BASELINE

The change from baseline value is defined as the value at a given time point minus the baseline value.

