5.4 DERIVED VARIABLES

ETDRS Score and LogMAR (on chart and off chart)

- ETDRS score is calculated by the examiner and written on the source documents and entered in the eCRF.
- LogMAR (on chart and off chart) will all be derived in eCRF from the Snellen/decimal acuity.
 - I. 1 ETDRS line = 5 letters
 - II. 1 ETDRS line = 0.1 LogMAR
 - III. 0.1 LogMAR = 5 ETDRS letters
 - IV. 15 ETDRS letters = 0.3 LogMAR
 - V. A less positive/more negative LogMAR is an improvement of vision
 - VI. An increase in the number of ETDRS letters read is an improvement of vision
- On-Chart subjects: defined as being able to read at least 3 ETDRS letters on a single line on the ETDRS chart at either 4 or 1 meters
 - a. Have an obtainable Snellen equivalent obtained directly from ETDRS chart

- b. Each Snellen equivalent is assigned a LogMAR value. A Snellen score of 6/6, 20/20, indicating that an observer can resolve details as small as 1 minute of visual angle, corresponds to a LogMAR of 0, since the base-10 logarithm of 1 is 0. A Snellen score of 6/12, 20/40, indicating an observer can resolve details as small as 2 minutes of visual angle, corresponds to a LogMAR of 0.3, since the base-10 logarithm of 2 is near-approximately 0.3, and so on.
- Off-chart subjects: defined as a subject who cannot read at least 3 ETDRS letters on a single line of the ETDRS chart at 1 meter and thus have no Snellen equivalent obtainable from ETDRS chart
 - a. These subjects are categorized as able to either count fingers (CF), detect hand motion (HM), detect light perception (LP), or are no-light perception (NLP).
 - b. If there is no CF and HM and a subject's visual acuity is light perception, then a LogMAR value of 4 will be assigned. If a subject's visual acuity is no light perception, then a LogMAR value of 4.5 will be assigned.
 - c. For those categorized as CF a LogMAR value of 2 will be assigned (Lange equivalence)
 - d. For those categorized as HM a LogMAR value of 2.3 will be assigned (Lange equivalence).

LogCS

Contrast sensitivity was assessed using the Pelli-Robson chart for low vision, on a scale from zero to 2.5 LogCS. Subjects who could not read at least 2 out of the first 3 letters on the Pelli-Robson chart will be assigned the worst possible score (a LogCS of zero).

- LogCS is obtained based on which letter triplets the subject can read correctly on the chart, and the LogCS value is then entered in the eCRF.

Nadir of LogCS

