8. STATISTICAL METHODS

All analyses will be performed on SAS Version 9.4 or higher.

Unless otherwise noted, categorical and binary variables will be summarized using counts and percentages. Percentages will be rounded to one decimal place.

Continuous variables will be summarized using the number of observations (n), mean, standard deviation (SD), median, first quartile (Q1), third quartile (Q3), minimum and maximum. Change from baseline or from nadir will also be summarized by a 95% confidence interval (CI).

Least square means, 95% CIs, and p-values will be reported from ANCOVA models. Estimated proportions with 95% CIs will be provided for Generalized Estimating Equation (GEE) models and for logistic regression models for responder endpoints. ANCOVA models will be run on all continuous endpoints, logistic regression for all subject responder endpoints, and GEE models for all eye responder endpoints.

Rounding rules are generally as follows:

- If the original variable has x decimal places, then minimum and maximum will be reported with x decimal places; mean, median, Q1, Q3, SD and CIs will be reported with x+1 decimal places.
- P-values will be reported with four decimal places.

Summary TFLs will display standard headers containing the sponsor name (“GenSight Biologics”) as well as a standard footer containing the name of the program used to generate the display, its path, and a date stamp. Headers, footers, titles, and column headers for tables will be repeated on every page of each display; pages will be numbered “Page x of y.” Visit labels in tables and figures will show visit name. Summary TFLs containing no applicable data will display a line reading, “No applicable data were reported” or similar wording. Dates and times will be presented using SAS DATE9. and SAS TIME5. formats.

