8.5.2 Secondary Efficacy Variables

8.5.2.1 Pelli-Robson Contrast Sensitivity

Eye Level

Contrast Sensitivity will be summarized at each follow-up visit (Years 2, 3, 4, and 5), along with change from baseline to each follow-up visit.

This summary will be done comparing all-GS010 eyes to all-sham eyes.

These summary tables will be reproduced for eyes with on-chart LogCS at baseline, with off-chart LogCS at baseline (equivalence LogCS 0), and for all eyes.

The change of LogCS from baseline to the visit of interest will be compared between all-GS010 treated eyes and all-Sham treated eyes.

At each visit of interest, the following analyses related to Nadir LogCS will be performed:

- The change from Nadir LogCS will be calculated for each eye of each subject and will be expressed in LogCS.
- The time to Nadir LogCS will be calculated for each eye of each subject and will be expressed in Weeks.
- The mean LogCS change from Nadir will be assessed for all eyes, all GS010 eyes and all-Sham eyes.
- The mean time to Nadir LogCS will be assessed for all eyes, all GS010 eyes and all-Sham eyes.

Subject Level

At subject level, the best outcome (change from Baseline or change from Nadir) observed in either eye will be considered. The following summaries will be presented:

- The change of LogCS from baseline to the visit of interest
- The change of LogCS from Nadir to the visit of interest

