8.5.2.2 LogMAR

Eye Level

Mean LogMAR BCVA will be summarized at each follow-up visit (Years 2, 2.5, 3, 4 and 5), along with mean change from baseline to each follow-up visit.

This summary comparing all-GS010 eyes to all-sham eyes will be repeated by comparing best-GS010 eyes to best-sham eyes and worst-GS010 eyes to worst-sham eyes.

These summary tables will be reproduced for those eyes with on-chart BCVA at baseline.

The curves of change from baseline at each time point for treated and sham eyes will be produced, with both sham and treated curves on same graph

The curves of absolute BCVA values at each time point for treated and sham eyes will be produced with both sham and treated curves on same graph.

LogMAR BCVA will be analyzed by using two approaches:

For the EMA, the change of LogMAR from baseline to the visit of interest will be compared between all-GS010 treated eyes and all-Sham treated eyes using a mixed-effects analysis of covariance (ANCOVA), with baseline LogMAR as a covariate, and subject and eyes of the subject as random factors.

The FDA has recommended comparing GS010 vs Sham in the Best-seeing eyes as a primary analysis. Therefore, change of LogMAR from baseline to the visit of interest will be compared between Best-GS010 treated eyes and Best-Sham treated eyes for the FDA. ANCOVA will be used for this analysis.

The EMA analysis is based on intra-subject comparison of change of LogMAR from baseline to the visit of interest. For FDA, the analysis is based on inter-subject comparison of change of LogMAR from baseline.

For eyes with on-chart BCVA at baseline, the change of LogMAR from baseline to the visit of interest will be analyzed between GS010-treated eyes and Sham-treated eyes.

At each visit of interest, the following analyses related to Nadir BCVA will be performed:

- The change from Nadir BCVA will be calculated for each eye of each subject and will be expressed in LogMAR.
- The time to Nadir BCVA will be calculated for each eye of each subject and will be expressed in Weeks.
- The mean LogMAR change from Nadir will be assessed for all eyes, all GS010 eyes and all sham eyes.
- The mean time to Nadir BCVA will be assessed for all eyes, all GS010 eyes and all sham eyes.

Subject Level

At subject level, the best outcome observed in either eye will be considered. The following summaries will be presented:

- The change of LogMAR BCVA from baseline to the visit of interest

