The following responders analyses will be performed on all eyes, all GS010 eyes and all sham eyes.

- Eyes with an improvement of at least 0.3 LogCS compared to baseline.
- Eyes with an improvement of at least 0.3 LogCS compared to nadir LogCS.
- For eyes with on-chart LogCS at baseline, an improvement of at least 0.3 LogCS compared to baseline.

- Switch from baseline off-chart LogCS to on-chart at visit of interest

Subject Level – Subject Responder

At subject level, the best outcome observed in either eye will be considered.

LogMAR

Subject Responder analyses will be carried out at visit of interest for the following definitions:

- Subjects with CRR from baseline in at least one eye at visit of interest.
- Subjects with CRR from nadir in at least one eye at visit of interest.
- Subjects with an improvement of at least -0.3 logMAR compared to baseline in at least one eye at visit of interest.
- Subjects with an improvement of at least -0.3 LogMAR compared to nadir in at least one eye at visit of interest.
- Subjects with an improvement of at least -0.2 logMAR compared to baseline in at least one eye at visit of interest.
- Subjects with an improvement of at least -0.2 logMAR compared to nadir in at least one eye at visit of interest.
- Subject with LogMAR BCVA value $\leq +1.0$ LogMAR in at least one eye at visit of interest.
- Subject with LogMAR BCVA value $< +1.0$ LogMAR in at least one eye at visit of interest.
- For patients with both eyes off-chart at baseline, switch from baseline to on-chart (LogMAR ≤ 1.6) in at least one eye at visit of interest
- Number/percentage of on-chart patients (at least one eye on-chart) at visit of interest
- Clinically Relevant stabilization (CRS): Patient having a LogMAR < 1.0 at baseline in at least one eye that was maintained in this eye at the time point of interest (final BCVA)
- Clinically Relevant Benefit (CRB): Treatment benefit manifests as a clinically relevant stabilization (CRS) or a clinically relevant recovery (CRR) from nadir or both

For the subject responder endpoint, a randomization test will be performed for each of the follow-up visits (Years 2, 2.5, 3, 4 and 5):

- Response status of subjects whose ETDRS scores of the treated eye are at least 15 letters better than the sham eye or whose treated eye has a LogMAR acuity of at least 0.3 LogMAR better than the sham eye at each long-term follow-up visit.

LogCS

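### The subject-level change from baseline keeps the better of the two eyes' changes, so its mean and 95% CI lean towards improvement

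*SAP*

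**What the plan says.** SAP 8.5.2.2 (LogMAR), under its subject-level heading, gives the rule: "At subject level, the best outcome observed in either eye will be considered". The first quantity then listed is "The change of LogMAR BCVA from baseline to the visit of interest". The contrast-sensitivity section, SAP 8.5.2.1, is more explicit: "At subject level, the best outcome (change from Baseline or change from Nadir) observed in either eye will be considered".

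Three other places complete the definition:

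- SAP 5.3: "The change from baseline value is defined as the value at a given time point minus the baseline value".
- SAP 5.4: "A less positive/more negative LogMAR is an improvement of vision". For LogMAR, the best of two changes is therefore the smaller (more negative) one.
- SAP 8: "Change from baseline or from nadir will also be summarized by a 95% confidence interval (CI".

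The responder section (8.5.2.4) applies the same either-eye rule to rates, for example "Subjects with an improvement of at least -0.3 logMAR compared to baseline in at least one eye at visit of interest".

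SAP 3.1 records that every subject had GS010 in one eye and sham in the other, so a subject-level summary has no control group. The protocol's LogMAR and contrast-sensitivity analyses (11.5.2.1 and 11.5.2.2) contain no best-of-either-eye change, and SAP 8.8 does not list it among the changes from the protocol.

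**The concern.** The eye that represents a subject is chosen after the outcome is known, and only at the follow-up end. Two changes are computed and the more favourable is kept, with no matching selection at baseline. Such a rule does not average to zero when nothing has truly happened, because whichever eye happened to be measured better at that visit is the one retained.

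With a 95% CI attached, the result looks like an estimate of mean change in vision. A reader who sees an interval clear of zero at Year 5 would naturally take it as lasting gain, and no untreated subjects exist to show how much of it the rule itself produces. The error always points the same way, in the product's favour.

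**Working it through.** **Plan's own figure.** There is none to reproduce. Neither document gives a sample size, an SD of change, a between-eye correlation or an expected subject-level change.

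**Inputs from the documents.** The selection rule, definition of change, direction of LogMAR and 95% CI are as above. One letter is 0.02 LogMAR (protocol 9.6.5). In the natural-history cohort, 14.7% of eyes and 18% of patients improved by at least 15 letters (protocol 5.1).

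**Assumed inputs.** SD of change s, between-eye correlation of change r, and number of subjects n, all shown as ranges.

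**Step 1: expected value under no mean change.** Let d1 and d2 be the two eyes' changes, bivariate normal with mean 0. Then min(d1, d2) = (d1 + d2)/2 − |d1 − d2|/2. The first term has mean 0. The difference d1 − d2 has SD s√(2(1 − r)), so E|d1 − d2| = 2s√((1 − r)/π). Hence

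- E[min] = −s√((1 − r)/π)
- Var[min] = s²(1 − (1 − r)/π)

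The bias is zero only if r = 1.

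| s (assumed) | r = 0.5 | r = 0.7 | r = 0.9 |
|---|---|---|---|
| 0.1 | −0.040 | −0.031 | −0.018 |
| 0.2 | −0.080 | −0.062 | −0.036 |
| 0.3 | −0.120 | −0.093 | −0.054 |
| 0.5 | −0.199 | −0.155 | −0.089 |

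For s 0.3–0.5 and r 0.5–0.7 the range is 0.093 to 0.199 LogMAR. Dividing by 0.02 gives about 5 to 10 letters.

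**Step 2: how often the 95% CI lies wholly on the improvement side.** Write m = √((1 − r)/π). The t statistic is approximately noncentral t with n − 1 degrees of freedom and noncentrality −√n × m/√(1 − m²). This does not depend on s. For r = 0.5 and n = 60: m = 0.399, √(1 − m²) = 0.917, noncentrality −3.37, probability 91%.

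| n (assumed) | r = 0.5 | r = 0.7 | r = 0.9 | r = 1 |
|---|---|---|---|---|
| 30 | 63% | 41% | 16% | 2.5% |
| 60 | 91% | 70% | 28% | 2.5% |

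**Step 3: calibration to the protocol's natural-history figures.** Assume zero-mean normal change.

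- P(change ≤ −0.3) = 0.147 gives 0.3/s = 1.049, so s = 0.286.
- P(both eyes improve) = 2 × 0.147 − 0.18 = 0.114, which gives r = 0.935.
- m = √(0.065/π) = 0.144, so the bias is 0.286 × 0.144 = 0.041 LogMAR, about 2 letters.
- At n = 60 the noncentrality is about −1.12 and the probability about 20%.

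**Step 4: subjects with no recorded change.** Count-fingers is fixed at 2.0 LogMAR and hand-motion at 2.3 (SAP 5.4). A subject whose recorded values are the same at both times in both eyes has a minimum of exactly 0 and adds no bias. The next simulation keeps true acuity stable with measurement error only (measurement SD 0.07–0.15, acuity SD 0.4, between-eye acuity correlation 0.8, all assumed). With 40% of subjects at exactly zero, the mean was still −0.033 to −0.060. The CI lay wholly on the improvement side in 40–79% of runs at n = 30 and 73–98% at n = 60.

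**Step 5: another reading of the LogMAR sentence.** If it means the change in the eye with the better acuity at the visit, the same simulation gave −0.008 to −0.040 LogMAR, with the CI wholly on the improvement side in 6–35% of runs. Other assumed settings (measurement SD 0.1, n = 60) gave −0.02 to −0.04 and 18–67%. The bias is smaller but in the same direction.

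**Step 6: same rule at both times.** Better-eye value at the visit minus better-eye value at baseline gave a simulated mean within 0.001 of zero, with the CI on the improvement side in 2–3% of runs, which is nominal.

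**The case against.** The strongest reply is about weight. The primary endpoint is safety, SAP 8.5.1 says there is no primary efficacy variable, and 8.5.4 makes all efficacy secondary. The item is a summary with no hypothesis or model attached. A reader might infer that the trial's treatment comparisons are biased too. They are not: the EMA analysis uses all GS010 against all sham eyes, and the FDA analysis uses eyes designated best-seeing at baseline (SAP 6.4). This stands, and it limits the point to a misleading estimate and interval.

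The LogMAR sentence does not itself say that the best outcome is the best change. That comes from the parallel contrast-sensitivity text. The reading is likely but not certain, and Step 5 shows that the main alternative reduces the bias without removing it.

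A reader might take 5 to 10 letters, or 70–91%, as established. The documents do not support that. Those figures need r of 0.5–0.7, whereas the only calibration available from the documents gives r near 0.94, about 2 letters and about 20%. Two letters is well below the SAP's own 0.2 and 0.3 LogMAR thresholds. The calibration is itself rough, since the natural-history figures describe improvement over a study period and not at one visit.

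Nor can the larger sizes be put down to measurement noise alone. An SD of 0.3–0.5 over years may contain real change, and the protocol describes limited spontaneous recovery. Where an eye has really gained, the summary correctly reports the best change in either eye. It misleads when read as mean change or as treatment benefit.

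Finally, eye-level GS010 and sham results are already planned at the same visits, including most counterparts of the at-least-one-eye responder definitions (8.5.2.4). A reader can consult them, so printing them side by side is a matter of layout. They do not correct the interval on the selected mean.

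**Conclusion.** The point holds for the subject-level change from baseline in contrast sensitivity (8.5.2.1) and, by the parallel wording, in LogMAR (8.5.2.2). With zero true mean change in both eyes and recorded changes that vary, the mean is shifted towards improvement by SD × √((1 − r)/π), and its 95% CI excludes zero on that side more often than 2.5%. The direction follows from the rule, while the size rests on SD, r and n, none of which is given. A plausible low case is the natural-history calibration (normal, zero-mean, n = 60): about 0.04 LogMAR and 20%. Assumed SD 0.3–0.5 and r 0.5–0.7 give 0.09–0.20 LogMAR and about 70–91% at the same n.

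It would go too far to say that the summary shows improvement whenever neither eye has changed: unchanged recorded values add nothing. It would also go too far to say that the study's efficacy conclusions depend on it. This is a should-fix for a descriptive secondary summary.

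**What to change.** In SAP 8.5.2.1 and 8.5.2.2, define subject-level change from baseline as the better-eye value at the visit minus the better-eye value at baseline, and put the 95% CI on that. Selection is then the same at both times and cancels under no change. Fixing the eye by its baseline acuity is not an equivalent remedy: regression to the mean moved the simulated mean by 0.008 to 0.042 LogMAR towards worsening.

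If the best-of-two-changes summary is kept, label it as selected on outcome, report it without a CI, and state that it is not to be read as mean change or treatment benefit. State in 8.5.2.2 what the best outcome refers to, so that it no longer has to be inferred from 8.5.2.1. List the change in SAP 8.8 with its date and reason, since SAP version 2.0 is dated 30 June 2022 and interim analyses were planned at Years 3 and 4.

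The cost is SAP wording and one derived variable per endpoint, with no new data. The subject-level gain will look smaller. The new measure can also miss a gain confined to the worse-seeing eye, which the eye-level tables still show.
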